**THIS STUDY DOES NOT REQUIRE BAYLOR IRB APPROVAL.**

### 1) Funding Source

The researchers' primary funding will come from Baylor St. Luke's Friends of Nursing Foundation. This foundation's aim is to support nurses in their professional practice development. They have no financial conflict of interest with the researchers or the researchers' institution.

### 2) Objectives and Hypothesis(es)

The project goal is to investigate the efficacy of proning COVID-19 hypoxemic patients who are hospitalized at Baylor St. Luke's in an acute care, telemetry-monitored unit. The researchers will be using a systematic approach to educate patients and staff about patient self-proning, implementing self-proning every 2 hours, and monitoring escalation of oxygen levels, as well as length of the study period.

**Objectives:** This study is intended to explore the effects of proning on non-ventilated COVID-19 hypoxemic patients hospitalized in a telemetry-monitored, acute care unit. In addition, the hope is to delay intubation and/or escalation of respiratory interventions, while contributing to the growing body of knowledge related to COVID-19 treatment and care.

**Hypotheses:** The researchers expect to see an improvement in oxygen saturation levels as evidenced by no escalation of respiratory care (i.e. higher levels of oxygen needed, transfer to higher level of care), resulting in shorter lengths of stay for the intervention population.

### 3) Background/Scientific Rationale and Significance

*Describe the relevant prior experience and gaps in current knowledge.*

Colloquially, proning has been propagated to increase oxygen saturation in patients in respiratory distress. Since the COVID-19 virus's primary symptomatology is respiratory in nature, proning has re-emerged as a viable option, and research is ongoing in the intensive care unit (ICU) patient population about its effectiveness. However, there has been minimal research around proning methodology in the alert, oriented, and independent patient who has

been confirmed COVID-19 positive and has been admitted to a non-ICU setting. Therefore this study aims to address this lack of evidence.

#### Describe any relevant preliminary data.

Kallet (2015) summarized the physiological mechanism that prone position improves oxygenation in moderate to severe ARDS patients. First, a prone position can make the dorsal region more elevated, which leads to evenly distributed tidal volume in the lung. Second, a prone position decreases the pressure that the lung receives from the heart and abdomen, which can increase resting lung volume in dorsocaudal regions. Third, when patients are in a prone position, the pressure from mass tissue in the dorsal wall can make pleural pressure more evenly distributed in the lung.

A meta-analysis with randomized controlled trials indicated that prone positioning became a life-saving intervention for mechanically ventilated ICU patients with moderate to severe ARDS when it is applied for at least 12 hours daily (Munshi et al., 2017). Ding et al. (2020) evaluated the outcome of intubation in ARDS patients whose average prone positioning (PP) was 2 hours. These patients received oxygen with high-flow nasal cannula (HFNC) and non-invasive ventilation (NIV), or only non-invasive ventilation. Ding et al. (2020) concluded that the prone position helped ICU ARDS patients avoid intubation when combined with other non – invasive oxygenation intervention in the early stage of ARDS. The results of a randomized controlled trial indicated that the outcome of early application of prone position in ICU ARDS patients demonstrated a significantly decreased 28-day and 90-days mortality (Guerin et al., 2013). The study included 466 patients from healthcare multicenters. The patients were divided into two groups, a prone group with 237 patients, and a supine group with 229 patients. The patients in the prone group were subjected to prone-positioning for at least 16 hours. In contrast, the patients in the supine group were left in the supine position. The study found a 28-day mortality; 16% in prone group vs. 32.8% in supine group (P, 0.001); hazard ratio for death was 0.39 in prone group vs. 0.44 in supine group (P, 0.001), and unadjusted 90-day mortality was 23.6% in prone group vs. 41.0% in supine group (P, 0.001) (Guerin et al., 2013). Based on the above evidence - prone positioning has been recommended by the World Health Organization (WHO) as one of the better interventions for mechanically ventilated patients with moderate-severe ARDS within ICU (World Health Organization, 2020). Cardona et al. (2021) in a meta-analysis of observational studies found ICU patients with COVID-19 with non-invasive oxygen interventions and awake prone positioning, the intubation rate was 28% and mortality rate was 14%.

Weatherald et al. (2021) reported that prone positioning promised an improvement in oxygenation while patients were in the prone position. The review included 35 studies with 414 patients from various clinical settings. Twenty-nine of these studies report on the use of awake prone positioning in COVID-19 patients. Among 35 studies, only one study included data from the control group. All studies demonstrated improvement in oxygenation while patients were in the prone position except one.

Another study of 50 patients in an ED setting reported that using an awake prone position in managing COVID 19 pneumonia showed some benefits in improving acute hypoxemia (Caputo et al., 2020). McNicholas et al. (2020)

emphasized that to date there is still a lack of randomized control trials that support the benefit of awake prone position on COVID-19 pneumonia patients with hypoxia. Furthermore, there was no study that revealed whether or not non-ventilated prone positions change mortality rate in patients with COVID-19 ARDS.

Proning has been attempted before in the healthcare setting. An emergency department (ED) in New York asked 50 patients to self-prone for 5 minutes, and recorded their oxygen saturation both before and after the intervention. This study saw an improvement of at least 10% in oxygen saturation across the sample, although 13 of those patients later had to be intubated within 24 hours of arriving at this ED (Caputo et al., 2020). Another study, conducted in non-ICU units in Italy, surveyed 50 patients confirmed with COVID-19, reported increased PaO2 levels from proning for 10 minutes, and those levels were able to be sustained after proning in approximately half the patients (Coppa, et.al., 2020).

Nursing clinicians Holland (2020) and McKenna et al. (2018) discussed the important role of nurse clinicians utilizing prone position therapy to promote positive patient outcomes. These authors describe clinician roles as initiating multidisciplinary discussions, helping to apply prone positions, educating on the technique of prone position, supporting patients who undergo prone positioning, and evaluating outcomes. Our nurse researchers aim to add to the body of evidence surrounding positive outcomes of proning in the acute care setting of non-intubated COVID-19 patients.

#### **4) Inclusion and Exclusion Criteria**

##### **Inclusion Criteria:**

The inclusion criteria for this research study are patients that have been confirmed COVID-19 positive on an acute-care, telemetry-monitored, non-ICU unit and are considered hypoxemic. Hypoxemic is defined as experiencing rising oxygen requirements as evidenced by increasing levels of supplemental oxygen (i.e. starting at 1-2 L nasal cannula and increasing oxygen need from that level, up to 6 L on nasal cannula.) The patient must also be conscious and oriented, as well as able to change positions independently (meaning that it would not take an increased amount of energy or effort to position independently. Subjects will be patients 18 years and older. If the patient is unable to speak, read, or write English, an alternative consent in their language will be utilized.

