##### **Exclusion Criteria:**

The exclusion criteria included those that are not COVID 19 positive. Those patients that are COVID -19 positive and in an ICU setting, or in need of ICU level respiratory treatments and interventions would be excluded, as well as those with respiratory distress (defined as immediate need for intubation, respiratory rate over 35, PaCO2 level above 65, and accessory muscle use) or in hemodynamic instability (systolic blood pressure below 90) or arrhythmia. The researchers would also exclude patients that have agitation or who have altered mental status, unstable spine/thoracic injury or recent abdominal surgery, significant pressure ulcers (above stage 1), pregnant patients past the 2nd trimester, and patients that have concerning neurological issues (such as seizures). Patients that are unable to change positions independently will also be excluded.

*Describe how individuals will be screened for eligibility.*

This is a single-center prospective study which will be conducted over a period of 8 months on a telemetry-monitored, acute care unit in a large tertiary teaching hospital in Houston, Texas. Randomized sampling will be used to recruit and consent 96 patients that meet the study inclusion criteria (48 in the intervention group and 48 in the control group). This study will seek approval from the Common Spirit Health Institutional Review Board, and all participants receiving the intervention will be consented (see consent form attached).

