## **7) Study Endpoints**

Primary endpoint of this study is a shorter length of stay for the intervention group. Secondary endpoints include decreased need for oxygen supplementation as evidenced by higher oxygen saturation levels, decreased need to be admitted to the intensive care unit, and decreased reports of pressure injuries (as identified by BSLMC protocol).

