## **8) Procedures Involved**

**Study Design:** This will be a prospective randomized cohort study in which data will be collected for over 14 days or until discharged or transferred to a lower level of care from the telemetry-monitored, acute care unit. Data collected on study participants will include the need for escalating respiratory care as well as length of stay in the acute care unit. Comparative analysis will be conducted with retrospective data collected from hospitalized patients (the control group) with a diagnosis of COVID-19 on a non-ICU acute care, telemetry-monitored unit that meets the hypoxemia criteria, but that will not receive the proning intervention. The data from the control group will be collected by a retrospective chart analysis after 14 days past their discharge date.

On a confirmed COVID-19 non-ICU acute care, telemetry-monitored unit, there will be two sets of patients: patients that will receive the intervention of proning plus standard of care, and patients that receive standard of care, but not the proning intervention. Confirmed COVID-19 positive patients are randomly assigned by bed control to a room upon admission to the unit. Patients will be randomized upon admission to the acute care, telemetry-monitored unit, and selected based

on inclusion criteria. The patients that will be prone will be identified by a door slot "slider" that is purple. Timing devices will be purchased and placed at the nurses' station, and checklists to indicate proning times will be placed inside the room with a patient identification sticker. The researchers will be following the proning protocol for acute care patients provided by CommonSpirit Health (CSH).

Patients will consent to participation (using an approved consent document from the CSH IRB), and an order for the proning protocol will be entered in the EMR by the physician. The patient will be educated about self-proning, and instructed to self-prone every 2 hours. The nursing staff will document patient position on the checklists every 2 hours.

1. Upon initiation of the initial proning, the patient will be monitored by the RN for adverse effects for 15 minutes (such as inability to tolerate position or signs of respiratory distress).

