2. If the patient tolerates the proning well, the procedure can continue and the RN will set the timer for 2 hours, enter the patient's oxygen saturation into the EMR, and document the position (prone or supine) on the checklist. O2 saturation will be documented at least every 4 hours per unit protocol.
3. The 2 hour timer will be reset each set of 2 hours by the nursing staff, and the intervention will continue until the end of the study period or until the patient is discharged or transferred from that unit.
4. The checklists will be placed in a binder at the nurses' station at the end of each shift and collected daily by a member of the research team.
5. This intervention for each "proned" patient will continue until either of the following occur: either the patient is discharged or transferred to a lower level of care from the acute care floor, or 14 days have passed.
6. A retrospective chart review will be completed by the research team to ascertain length of stay on the acute care, telemetry monitored unit, as well as the need for escalation of respiratory care. Escalation is defined by a need for oxygen requirements above 6 liters of oxygen on the nasal cannula.

*If the patient is assigned to the control group, that patient will receive the standard of care treatment designated by BSLMC policy per their condition on the COVID-19, acute care, telemetry-monitored unit.*

**Data Analysis:** Retrospective data analysis will be conducted by the research team with data collected from the electronic medical record as well as the checklists (oxygen saturation, demographics, proning protocol) for both the interventional and control group. See attached documents for consent/proning protocol documents.

This study will be a prospective cohort study in which data will be collected on subjects for the designated time period. Data will be collected from the electronic medical record as well as the checklists. Data collection will include basic patient demographics, specifically age and gender, height, weight and ethnicity. Clinical data to be collected include O2 saturation, respiratory support methods, proning duration/compliance, presence of hospital acquired pressure injuries,

and need to escalate care to ICU, including initiation of mechanical ventilation. The same data will be collected for the control group - except for proning duration/compliance as they will not receive this intervention.

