### ***Waiver or Alteration of the Consent Process***

For our patients assigned to the control group, a waiver of consent will be requested.

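### Eligibility limits and escalation outcomes meet at the same oxygen and ICU cut, but the protocol fixes no common time at which eligibility is judged in the two arms

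*Protocol*

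**What the plan says.** **Entry limits (Protocol, Section 4).** Hypoxemia is defined by a rising need for supplemental oxygen, "starting at 1-2 L nasal cannula and increasing oxygen need from that level, up to 6 L on nasal cannula". Patients already in an ICU, or "in need of ICU level respiratory treatments and interventions would be excluded".

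**Outcomes (Protocol, Sections 7 and 8).** Step 6 of Section 8 reads: "Escalation is defined by a need for oxygen requirements above 6 liters of oxygen on the nasal cannula". Section 7 lists "decreased need to be admitted to the intensive care unit" among the secondary endpoints. The primary endpoint is length of stay, analysed in Section 10 as time to discharge from the unit.

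**How proned patients enter (Sections 15 and 18).** Assignment is confirmed, a physician's order is entered, and a research-team member explains the study and takes consent at the bedside.

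**How controls enter.** Section 8 gives two accounts. One describes assignment at admission: "Patients will be randomized upon admission to the acute care, telemetry-monitored unit, and selected based" on the inclusion criteria. The other describes a comparison with "retrospective data collected from hospitalized patients (the control group) with a diagnosis of COVID-19" who meet the hypoxemia criteria, and adds: "The data from the control group will be collected by a retrospective chart analysis after 14 days past their discharge date". Section 18 says: "For our patients assigned to the control group, a waiver of consent will be requested". No consent event therefore dates a control's entry.

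**What is collected.** Section 8 says controls will have the same data as proned patients, apart from proning duration and compliance. Those data include escalation to ICU care and mechanical ventilation.

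**The concern.** The entry ceiling and the escalation outcome are complements on one scale: 6 L or less to enter, more than 6 L to have the event. The ICU-need exclusion and the ICU endpoint stand in a similar relation. The same chart entry can therefore make a patient ineligible or count as an outcome, depending only on whether it falls before or after the moment eligibility is judged. The protocol does not state that moment.

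For proned patients the bedside process supplies one in practice. For controls nothing does, and on the retrospective account the whole oxygen course is visible when the chart is opened. Two abstractors reading the criteria at different points in the same charts would build different control groups. The two arms could also differ in who is allowed to have escalated, which affects the escalation and ICU comparisons directly and time to discharge indirectly.

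**Working it through.** **1. Is any eligibility time stated?** The only named time is randomization on admission (Section 8). It cannot serve reliably as the reading time, because the criterion is an oxygen need that has risen from a 1-2 L start, and a patient may not show that on arrival. The same sentence goes on to selection on the criteria without saying when. The 14-days-past-discharge rule says when control data are collected, not when eligibility is assessed.

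**2. Two ways the arms can diverge.**

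- *Against proning.* Eligibility is read over the finished control chart. A control who went from 2 to 4 to 8 L is judged to have passed the ceiling and is dropped. A proned patient with the same course is kept, because step 5 of Section 8 ends the intervention only at discharge, step-down or 14 days.
- *In favour of proning.* A patient assigned to proning escalates between assignment and consent and never enters. The matching control has no consent step and is kept.

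**3. Size, as illustration only.** The protocol gives no escalation rate, so the rate is an assumption. Let *p* be the true escalation proportion in both arms and *f* the fraction of escalated patients lost from one arm. That arm then reads

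p(1 − f) / (1 − p·f).

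| Assumed p | f = 0.25 | f = 0.5 | f = 1 |
|---|---|---|---|
| 10% | 7.7% | 5.3% | 0% |
| 20% | 15.8% | 11.1% | 0% |
| 30% | 24.3% | 17.6% | 0% |

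For p = 0.30 and f = 0.5: 0.15 / 0.85 = 0.176, against 30% in the other arm, a ratio of 0.30 / 0.176 = 1.70 with no true effect. The formula is the same whichever arm loses patients. If controls are lost, proning looks harmful. If proning candidates are lost before consent, proning looks protective.

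**4. Primary outcome.** Null simulations used 48 per arm, 30% escalation and a log-rank test at 1.96 in either direction, with escalated controls lost. The percentages are the chance of a false finding when half, then all, are lost; with none lost it is about 2.5 to 3% in each direction.

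| Assumed stay of escalated patients | False finding | Half lost | All lost |
|---|---|---|---|
| Three times as long (others: median 6 days, exponential; 14-day censoring) | Longer stay with proning | about 7-9% | about 25% |
| Median 10 days against 5 (log-normal, log-SD 0.5; 14-day cap) | Longer stay with proning | about 12% | about 55% |
| Leave the unit on days 1-4, censored then (others as in row 2) | Longer stay with proning | about 3-4% | about 5% |
| Leave the unit on days 1-4, counted as end of unit stay (others as in row 2) | Shorter stay with proning | about 10% | about 37% |

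The same loss of controls changes sign with the assumed handling of patients who leave the unit. The protocol supports no figure for the primary outcome.

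**The case against.** The strongest reply is that the criteria read naturally as states at entry. Section 4 speaks of patients experiencing rising requirements and of an immediate need for intubation. A patient who went from 2 to 4 to 8 L did meet the definition at 4 L, and a ceiling that complements a later outcome is ordinary design. This stands. The overlap alone is not the defect; the missing reading time, with two arms assembled differently, is.

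Second, the plan to collect ICU escalation and ventilation for controls suggests that escalated controls are meant to be kept. If they were all screened out, that field would always be empty. This also stands, and it makes total removal an implausible reading. It does not say at what point a control becomes eligible, so partial or inconsistent removal remains possible.

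Third, Section 8 also describes randomization on admission, and Sections 8 and 18 refer to patients assigned to the control group. So it cannot be stated as fact that controls are picked from finished charts. The two accounts conflict, and on either one selection on the criteria has no stated time.

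A reader might infer that the written criteria themselves remove escalated controls and so bias the trial against proning by a calculable amount. The protocol does not support that. It would take a misapplication of the criteria, the opposite bias is equally open, and oxygen above 6 L is a chart-review item in step 6 rather than an endpoint listed in Section 7, with no test specified for it.

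**Conclusion.** The point holds as a gap in design. The 6 L and ICU limits in Section 4 are the complement of the escalation and ICU outcomes, no section fixes when they are read, and the arms share no time zero. Section 8's conflicting accounts of the control group leave open whether a control's eligibility is judged live or from a completed chart.

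The direction and size of any resulting bias cannot be derived from the protocol. The control rate of about 18% against 30% shows only what losing half of the escalated patients from one arm would do, and both the 30% and the half are assumptions. No claim is made about the size or sign of an effect on time to discharge. The change should be made because it is cheap and removes a discretion that could bias the comparison either way.

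**What to change.** In Sections 4 and 8 of the protocol:

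1. Reconcile the randomized and retrospective descriptions of the control group, and state one.
2. Define one index time applied identically in both arms. A workable choice is the first daily research-team screening at which the patient meets all criteria on the unit; Section 15 already places a team member there each day. The first charted flow above the 1-2 L starting level would be a poor choice on its own: proned patients must stay eligible through order and consent, so early escalators would be lost from that arm only.
3. Judge every criterion only from entries at or before the index time. Start time to discharge there, and count escalation and ICU need only after it.
4. Remove no patient in either arm for later events.
5. Log patients assigned to proning who escalate between the index time and consent, and handle them as controls are handled. One way is to require controls to be still eligible after the same index-to-consent lag, with follow-up in both arms then starting at the end of that lag.

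The cost is a few sentences, one timestamp field and a simple screening log. It needs no extra patients or procedures and changes no clinical rule.
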